10.4.5. Blinding

All PFSs will have the same external appearance and composition.

A list of subjects randomization codes will be generated by LSK global PS (an electronic version will be stored in a secure locked area). The list of patient randomization codes will be generated using PROC PLAN in the SAS[®] procedures. A stratified block randomization approach will be used for the randomization with stratification factor of country and study site. This list will identify each patient by randomization number and include the patient's corresponding treatment assignment. The randomization codes will be provided in a secure manner to the IWRS developer and the study drug packaging provider.

When the maintenance of the safety and well-being of the patient, as assessed by the Investigator, requires that the administered study treatment be revealed, the Investigator shall break the blind. Before a study drug is unblinded, every attempt should be made to discuss the case with the Sponsor to evaluate whether or not to break the blind. Unblinding will be done through the IWRS system. Accessing the IWRS for emergency unblinding should be done only in an emergency that necessitates identifying the study drug for the welfare of the patient.

An explanation for breaking the blind will be recorded in the relevant source documents. Breaking the code at the investigative study center will immediately disqualify the patient from further participation in the study.

10.4.6. Prior and Concomitant Therapy

10.4.6.1. Drug Interactions

No evidence of interaction of epoetin with other drugs was observed in the course of clinical trials. However, since cyclosporine is bound by RBCs there is potential for a drug interaction. If Eprex[®] is given concomitantly with cyclosporin, blood levels of cyclosporin should be monitored and the dose of cyclosporin adjusted as the hematocrit rises. An increase in heparin dose during hemodialysis is frequently required during the course of therapy with Eprex as a result of the increased packed cell volume. Occlusion of the dialysis system is possible if heparinization is not optimum.

There is no rescue medication or procedure as this is not a placebo controlled trial.

10.4.7. Treatment Compliance

A monitor of the Sponsor (or the delegate) will review the pharmacy records at each center including the Drug Dispensing Record Form on which the pharmacist or delegated person should record all study drug released for patient use. The monitor will compare the dispensing record and PFSs to the individual subject's identifiers and visit schedule to assure that the subject receives the correct treatment, dose, and that the dosing schedule is correct. The monitor's report will include details of any missed doses, errors in dose, treatment errors or schedule errors and reasons for these. All supplies and pharmacy documentation must be made available throughout the trial for the monitor to review.

10.4.8. Expected Adverse Events and Precautions for Use

In larger overseas clinical studies of erythropoietin products conducted among patients with renal failure, a number of treatment-related side effects have occurred. Hypertension (24.7%) was the most commonly reported side effect, followed by muscle cramp, upper respiratory infection and headache, respectively reported in about 20% of subjects. Other frequently reported events were different types of infections, thrombosis (associated with hemodialysis in patients with renal failure), diarrhea, hypertension, dizziness, weakness, etc. whose incidence ranged 6~16%. Epileptic seizure was rarely reported at an incidence of 0.6%. In addition, a potential risk of infection with fatal pathogens such as

virus is suggested with the use of currently marketed erythropoietin products, which may be contaminated with animal-derived proteins during their cell culture process. Thus, the adverse events described above may occur during this clinical study. Based on the labeling information of Espogen Prefilled Syringe, a list of expected adverse events and precautions for use in this clinical study is prepared as follows:

10.4.8.1. Expected adverse events

Anaphylaxis: Rarely, anaphylactic shock may occur. A potential event should be confirmed with close monitoring and then appropriate measures such as treatment discontinuation should be taken.

- 1) Cardiovascular: Increased blood pressure, vascular access thrombosis, and occasionally, palpitation may occur.
- 2) Hypertensive encephalopathy: A sudden increase in blood pressure may lead to hypertensive encephalopathy, manifested by headache, disturbances of consciousness, seizure, etc. and further to cerebral hemorrhage. The investigational product should be administered under the close monitoring of blood pressure, hematocrit, etc.
- 3) Cerebral infarction: An event of potential cerebral infarction should be confirmed with close monitoring. If confirmed, appropriate measures such as treatment discontinuation should be taken.
- 4) Skin: Occasionally, itching, skin rash, etc. may occur.
- 5) Liver: Occasionally, hepatic dysfunction such as increases in AST, ALT, LDH, ALP, total bilirubin, etc. may be observed.
- 6) Gastrointestinal: Occasionally, nausea, vomiting, loss of appetite and diarrhea may occur. Abdominal cramp may also occur.
- 7) Blood: Occasionally, increased leukocyte and increased eosinophil may occur. A decreased granulocyte may sometimes be observed in preterm neonates. In occasional cases, serum potassium, BUN, creatinine and uric acid may increase. Rickets may sometimes develop in preterm infants.
- 8) Others: Bleeding inside the eyes, enlarged inner wall of nose, nose bleed, edema, and occasional events of headache, dizziness, fever, slight fever, hot flash, general malaise, arthralgia, myalgia, bitter taste, convulsion and periorbital edema may occur.
- 9) The investigational product is generally well tolerated. The adverse reactions reported are frequent sequelae of the underlying disease and are not necessarily attributable to the investigational product.

10.4.8.2. Contraindications

The administration of investigational product is contraindicated in patients:

- 1) with known hypersensitivity to any component of the investigational product
- 2) with uncontrolled hypertension
- 3) with known hypersensitivity to mammalian cell-derived products or human albumin products
- 4) who develop pure red cell aplasia (PRCA) following treatment with any erythropoietin product

10.4.8.3. Precautions for use

- 1) Hypertensive patients (Confirmed hypertensive episodes have been reported with the use of investigational product. Hypertensive encephalopathy may occur)
- 2) Patients with a history of drug hypersensitivity
- 3) Patients with a predisposition to allergy
- 4) Patients at a risk of thromboembolic event due to current or history of myocardial, pulmonary or cerebral infarction (An increase in blood thickness has been reported with the use of investigational product. Thromboembolism may develop newly or may be exacerbated. Especially, when the investigational product is used to facilitate autologous blood collection or in the post-operative period where clot-formation tends to increase, a close monitoring is required).

- 5) Preterm infants with intraventricular hemorrhage or intracranial hemorrhage (cerebral hemorrhage may be exacerbated with the use of investigational product).
- 6) Patients with ischemic vascular disease
- 7) Patients with a history of seizure
- 8) Cancer patients

10.5. STUDY PROCEDURES

10.5.1. Screening Assessments

10.5.1.1. Demographic information

Subject demography information will be collected at the Screening and includes date of birth (or age), sex, race/ethnicity, subject initial and duration and quantity of smoking and alcohol ingestion.

10.5.1.2. Medical and Surgical History

Medical and surgical history and current medical conditions (including anemia of chronic renal failure history) will be recorded at the Screening Visit. All pertinent medical and surgical history within 6 months (in case of malignancy; 5 years) must be noted in the Medical History and Current Medical Conditions in eCRF.

10.5.1.3. Prior Medication History

All medications the patient is taking at the time of study entry (Visit 1) and has taken within 6 months before entry must be recorded on the concomitant medication page in the eCRF. Thereafter, any changes in concomitant medications or new medications added will be recorded in the eCRF.

10.5.2. Efficacy Assessments

10.5.2.1. Hemoglobin Level

Hemoglobin level will be measured via hematologic examination from a blood sample, and will be recorded on a biweekly basis on eCRF. The target range of hemoglobin level is 10.0 to 12.0 g/dl.

10.5.2.2. Individual Dosage

Individual dosage will be recorded on a biweekly basis on eCRF, and doses must be individualized to ensure that hemoglobin is maintained within the target range for each subject.

10.5.2.3. Hematocrit Level

Hematocrit level will be measured via hematologic examination from a blood sample, and will be recorded on a biweekly basis on eCRF.

10.5.2.4. Blood Transfusion

During the study, incidence of blood transfusion will be compared between the two treatment groups.

10.5.3. Safety Assessments

The items below will be assessed and the results should be recorded in the followings: (1) source documents and (2) eCRFs. If any “new abnormal finding” considered clinically significant at the Investigator’s discretion on any of the tests below or “aggravation” of the existing disease is observed after the subjects signs the informed consent form, an adequate treatment will be provided for the subject as needed. This case will be surveyed and assessed as an adverse event according to Section 9.5.3.3. Reporting Adverse Events. Any adverse event which did not disappear by the end of the study will be followed up.

10.5.3.1. Adverse Events

Any untoward medical occurrence in a patient or clinical investigation subject administered a pharmaceutical product and which does not necessarily have a causal relationship with this treatment. An adverse event (AE) can therefore be any unfavorable and unintended sign (including an abnormal laboratory finding), symptom, or disease temporally associated with the use of a medicinal (investigational) product, whether or not related to the medicinal (investigational) product (see the ICH Guideline for Clinical Safety Data Management: Definitions and Standards for Expedited Reporting).

In order to ensure complete safety data collection, all AEs or undesirable experiences occurring during the study (i.e., after signature of the Informed Consent), including any pre-and post-treatment periods required by the protocol, must be reported even if no investigational product was taken but specific study procedures were conducted.

Examples of AEs are as follows:

- Changes in the general condition of the subject
- Subjective symptoms offered by or elicited from the subject
- Objective signs observed by the Investigator or other study personnel
- All concurrent diseases that occur after the start of the study, including any change in severity or frequency of preexisting disease.
- All clinically relevant abnormalities in laboratory values or clinically relevant physical findings that occur during the study

Signs or symptoms of anemia should be recorded as AEs only if their nature changes considerably or their frequency or intensity increases in a clinically significant manner as compared to the clinical profile known to the Investigator from the subject’s history or the baseline period (observation period)..

Adverse findings that are not considered clinically relevant based on medical judgment that are related to routine clinical laboratory evaluations, vital signs, or physical examinations should not be recorded on the AE reporting page of the eCRF. These findings should instead be recorded on the designated eCRF page.

Causality Assessment

For all AEs, the Investigator must provide an assessment of causal relationship to study drug. The causality assessment must be recorded on the appropriate AE reporting page of the subject’s eCRF.

Not related: The relationship is unlikely or not related; i.e., there is no strong temporal relationship, and/or use of other drugs, underlying diseases, or other factors provide plausible explanations for the event or the subject did not take study drug.

Related: There is a possible or probable relationship; i.e., there is a reasonable or strong temporal relationship, and the events are unlikely attributed to other drugs, underlying diseases or other factors.

Severity Assessment

The Investigator will provide an assessment of the severity of each AE by recording a severity rating on the appropriate AE reporting page of the subject's eCRF. Severity is a description of the intensity of manifestation of the AE.

Severity will be assessed according to the following scale:

Mild: means awareness of symptoms or signs, but easily tolerated (acceptable).

Moderate: means enough discomfort to interfere with usual activity (disturbing).

Severe: means incapacity to work or to perform usual activities (unacceptable).

10.5.3.2. Serious Adverse Events

A Serious Adverse Events (SAE) is any untoward medical occurrence that occurs at any dose in any of the following outcome:

- results in death or is life-threatening
- requires inpatient hospitalization or prolongation of existing hospitalization
- results in persistent or significant disability/incapacity, or
- is a congenital anomaly/birth defect
- is medically important

In this context, the term life threatening refers to an event in which the subject was at immediate risk of death at the time of the event; it does NOT refer to an event which might have caused death if it would have been more severe.

Any important medical event that may not be immediately life threatening or result in death or hospitalization but, based upon appropriate medical judgment, may jeopardize the subject or may require medical or surgical intervention to prevent one of the other outcomes listed in the definition above should also be reported as a SAE. Examples of such events are intensive treatment in an emergency room or at home for allergic bronchospasm, blood dyscrasias or convulsions that do not result in hospitalization; or development of drug dependency or drug abuse.

Hospitalization for diagnostic or therapeutic procedures in the absence of any associated AE will not be considered as a SAE. If a hospitalization is planned prior to the subjects receiving the first dose of the investigational drug, it will not be classified as either an AE or SAE. This also applies to situation of scheduled elective surgery where no AE is present. Non-complicated, preplanned elective surgery

will not be considered an AE or SAE even if it involves hospitalization. However, if a hospitalization is unplanned or is a result of an AE, this will be considered an SAE.

Cases involving cancer as an Adverse Event could be reported as serious using the criterion “medically important”. Furthermore, emergency room visits that do not result in admission to the hospital will not be evaluated as SAEs.

Special Situation: Exposure to Study Drug during Pregnancy. Study personnel must report every pregnancy as soon as possible (within 24 hours after notification), even if no AE has occurred, and follow it to term. Investigators must instruct female subjects to inform them immediately should they become pregnant during the study. A subject who becomes pregnant during the study will immediately be discontinued (immediate stop of investigational product intake). The pregnancy will be registered in the Pregnancy Form to be completed with all available information and sent within the same time frame and following the same routing as for an SAE, as described below. The Investigator will make every effort to obtain all information related to the pregnancy and its final outcome; follow-up after the study has ended may be necessary.

All pregnancies that occurred during the study but only came to the knowledge of the Investigator after the termination of the study will be reported to the Sponsor or designee as if it occurred during the study. The same procedures specified above will be followed.

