10.5.3.3. Reporting Adverse Events

The Sponsor (or the delegates) must be informed about an SAE within 24 hours of the site knowing about the event. The Investigator must promptly forward to the Sponsor (or the delegates) a duly completed Investigator SAE Report Form for Development Drug provided by the company, even if the data are incomplete or if it is obvious that more data will be needed to make any conclusions.

Additional information (e.g. autopsy or lab reports) should be provided to the Sponsor in a timely fashion to ensure accurate follow-up of each case.

The Sponsor (or the delegates) will communicate safety information and Suspected Unexpected Serious Adverse Reactions – SUSARs) to the appropriate agency (ies) and all active Investigators, in accordance with applicable regulatory requirements. The appropriate IRB/IEC will also be informed by the Investigator or the Sponsor, as specified by the applicable regulatory requirements in the Korea Food and Drug Administration (KFDA) or the appropriate agency (ies). Investigators are to retain evidence of such IRB/IEC notification in their study binder.

A copy of the Investigator SAE report form and the completion guide will be provided to the Investigator.

If known by the Investigator, Serious Adverse Events up to 30 days after the final study visit must be reported to the Sponsor, even if the Investigator is certain that they are in no way associated with the study drug.

Adverse Events that the Investigator thinks may be associated with the study medication must be reported to the Sponsor regardless of the time between the event and the end of the study.

Follow-Up Procedures for Serious Adverse Events

The Sponsor shall promptly investigate all safety information received by it. Follow-up information to a safety report shall be submitted as soon as the relevant information is available.

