Relevant information such as discharge summaries, autopsy reports, and medical consultations shall be reviewed in detail by the Investigator. The Investigator shall comment on any event, abnormal laboratory result, or any other finding, noting whether it shall be considered a serious or nonserious AE or considered part of the subject's history. In addition, the Investigator shall report on an SAE form all subsequent events or other findings determined to be relevant and shall state for each event or finding whether it is related to study drug. All events determined to be nonserious shall be reported on the relevant eCRF page.

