10.6.5.2. Adverse Events

An AE that occurs during the treatment period will be considered a TEAE if it was not present prior to the first dose of study drug or was present prior to the first dose of study drug but increased in severity during the treatment period. If the same AE is reported more than once prior to the first dose of study drug, the AE with the greatest severity will be used as the benchmark for comparison with the AEs occurring after the first dose of study drug that were coded to the preferred term.

All AEs will be classified by System Organ Class (SOC) and Preferred Term (PT) according to Medical Dictionary for Regulatory Activities (MedDRA). If more than one AE is coded to the same preferred term for the same patient, the patient will be counted only once for that preferred term using the most severe and most related occurrence for the summarization by severity and by relationship to the study drug.

The number, percentage and the corresponding 95% CI of patients experiencing TEAEs in each treatment group will be presented. The significance test for treatment difference will be carried out using χ^2 -test or Fisher's exact test.

Listings will be presented for patients with SAEs, patients with AEs leading to permanent discontinuation, and patients with AEs leading to death.

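### The SAE definition contradicts itself for important medical events treated intensively in an emergency room without admission, which affects 24-hour notification and the SAE listing

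*Protocol*

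**What the plan says.** Section 10.5.3.2 lists the seriousness criteria. Hospitalization is one. Separate criteria cover events that are life-threatening and any event that "is medically important". A later paragraph expands the last of these: an important medical event that may jeopardize the subject, or may need intervention to prevent a listed outcome, "should also be reported as a SAE", even when it does not lead to hospitalization. The examples include "intensive treatment in an emergency room or at home for allergic bronchospasm, blood dyscrasias or convulsions that do not result in hospitalization".

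The section then sets out what does not count: hospitalization for procedures with no associated adverse event, hospitalization planned before the first dose, and uncomplicated preplanned elective surgery. After a sentence saying that cancer may be reported under the medically-important criterion, it ends with: "emergency room visits that do not result in admission to the hospital will not be evaluated as SAEs".

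Three later provisions depend on the classification:

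- Section 10.5.3.3: the sponsor "must be informed about an SAE within 24 hours of the site knowing about the event". SAEs known to the investigator up to 30 days after the final visit must be reported even if considered unrelated. For events that do not qualify as serious, the rule is "All events determined to be nonserious shall be reported on the relevant eCRF page".
- Section 10.5.3.3 also governs the communication of suspected unexpected serious adverse reactions to agencies and investigators.
- Section 10.6.5.2 plans a listing of patients with SAEs. Its between-group analysis is of treatment-emergent adverse events: "The number, percentage and the corresponding 95% CI of patients experiencing TEAEs in each treatment group will be presented", followed by a chi-square or Fisher test.

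**The concern.** The same event can satisfy the important-medical-event paragraph and be ruled out by the closing sentence, and the protocol does not say which prevails. Safety is the secondary objective and long-term safety is the aim of the extension (section 8). Section 7.4 states that PDA10 has not been used before in patients with chronic renal failure and relies on strict safety monitoring. The class of event at issue includes some that section 10.4.8.1 anticipates, such as convulsion and anaphylaxis, and these can be treated in an emergency room without admission. If the closing sentence is applied as written, medically important events follow the nonserious route. With about 20 centers in two countries (section 6), different sites may read the section differently.

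**Working it through.** The protocol states no figure on this point, so the check is a comparison of the text, followed by a rough scale.

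**1. Where the two rules meet (section 10.5.3.2).**

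| Event | Important-medical-event paragraph | Closing sentence |
|---|---|---|
| Convulsion, intensive emergency-room treatment, not admitted | SAE | Not an SAE |
| Same convulsion, admitted | SAE (hospitalization) | Silent |
| Same convulsion, intensive treatment at home | SAE | Silent |
| Minor complaint seen in an emergency room, sent home | Not an SAE | Not an SAE |

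Only the first row conflicts. Read literally, the closing sentence would also displace the life-threatening criterion, for instance for an anaphylactic reaction reversed in an emergency room without admission.

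**2. Whether the wording limits the closing sentence.** The neighbouring exclusions each carry a condition: no associated adverse event, planned in advance, or uncomplicated. The emergency-room sentence carries none. It follows a sentence about the medically-important criterion, so a site can fairly read it as limiting that criterion.

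**3. What changes with the classification.**

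- Sponsor notification: the 24-hour clock applies to SAEs; a nonserious event goes to the eCRF page.
- Expedited reporting: it requires the event to be serious, unexpected and suspected to be related. Losing the serious label matters here only if the other two hold.
- Post-study window: an SAE within 30 days of the final visit is reported whatever its cause. Outside the SAE rule, section 10.5.3.3 requires a report after the study only if the investigator thinks the event may be associated with the medication. For an event thought unrelated, the label can decide whether it is reported at all.
- SAE listing (section 10.6.5.2): its content changes.

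**4. What does not change.**

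- The by-group percentages, confidence intervals and test are on treatment-emergent events whatever their seriousness, so an event counts the same under either sentence.
- The maintenance phase is double-blind and randomization is stratified by country and site (section 10.4.5). A site's reading therefore falls on both arms alike in expectation.
- All extension patients receive PDA10 (section 10.2), so that phase has no comparator.

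**5. Scale, for one event type.** Inputs: seizure incidence 0.6% (section 10.4.8, from other studies) and 316 planned patients (section 10.6.7.1).

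Expected patients with a seizure = 0.006 × 316 = 1.9, both arms together.

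The share treated in an emergency room and not admitted is not given. Taking it from 0 to 100%, the number affected is 0 to about 1.9. This assumes that the quoted incidence applies here, although this trial excludes epilepsy and uncontrolled hypertension (section 10.3.2) and section 10.4.8 gives no follow-up time for the rate.

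**The case against.** The strongest reply is that the sentences can be reconciled. The definition is of an untoward occurrence meeting any one criterion, and the life-threatening and medically-important criteria do not depend on hospitalization. The closing sentence speaks of visits and ends a run of exclusions mostly about what counts as hospitalization. It may mean only that an emergency-room visit is not a hospitalization. Sites also receive an SAE completion guide (section 10.5.3.3), which is not shown and may say so. This reading is reasonable, but the protocol does not state it and the wording does not force it.

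The reply is right about several stronger conclusions that a reader might draw:

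- *That every emergency-room event without admission is classified both ways.* The first rule covers only important medical events; its example is intensive treatment.
- *That the safety comparison between arms depends on the reading.* The planned test is on treatment-emergent events regardless of seriousness. For SAEs the protocol plans a listing and no between-group test.
- *That these events would generally be lost from reporting of suspected unexpected serious reactions.* Section 10.4.8.1 lists anaphylactic shock, hypertensive encephalopathy with seizure, and convulsion as expected, so such events largely fall outside that route under either sentence.
- *That the 24.7% hypertension figure in section 10.4.8 shows how many events are at stake.* It is the incidence of a common side effect, not of serious events or emergencies. Applied to 316 patients it would give about 78 (0.247 × 316), which says nothing about emergency-room treatment without admission.
- *That site practice will differ.* The text permits this; it does not show it.

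**Conclusion.** The contradiction is real, lies in current text, and is narrow. It concerns important medical events treated intensively in an emergency room without hospitalization and, on a literal reading, life-threatening ones handled the same way. The fault is a rule stated wrongly within the section, not a detail left for another document.

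The consequence is possible under-reporting and inconsistency between sites in 24-hour notification, in the 30-day post-study capture and in the SAE listing. Expedited reporting is touched only for events that are also unexpected and suspected to be related. The primary endpoints, the power and the test on treatment-emergent events are untouched, and blinding with site stratification gives no reason to expect bias toward one arm.

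The number of events affected cannot be derived from the protocol. The seizure range of 0 to about 1.9 patients is an illustration that rests on an incidence from other studies and an unknown share not admitted.

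**What to change.** Reconcile the two sentences in section 10.5.3.2 so that the closing one agrees with the section's own list of seriousness criteria. One wording that would do so: an emergency-room visit without admission does not by itself meet the hospitalization criterion; the underlying event is still an SAE if it meets any other criterion listed above. This adds no new criterion.

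Bring the SAE completion guide into line at the same time, and tell sites of the clarification. The cost is one sentence in a protocol amendment and a matching edit to the guide. The planned analyses and the sample size do not change.
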